10. STUDY DESIGN

This RCT will compare insertion of a palliative tunnelled long-term abdominal drain (LTAD) (Group 1 intervention) to standard of care (Group 2 large volume paracentesis (LVP) in the management of refractory ascites due to advanced cirrhosis.

This is a multi-centre, non-blinded parallel-group RCT with up to 3 months of follow up and will be conducted across 35 sites in England and Scotland. We aim to recruit 310 patients.

Thirty patients, 20 informal caregivers and 20 HCP will also be invited to give their perceptions/perspectives of LTAD and LVP using qualitative methods.

An 18-month internal pilot will assess recruitment and LTAD safety: 12 months recruitment, three months' follow up, one-month for analysis, two-months' for a STOP/GO decision.

11. STUDY SETTING

National Health Service (NHS) Acute Hospitals and their corresponding Community Trusts to provide home care support to the participants with a LTAD (home drain). Sites will complete feasibility assessments to ensure they have the patient population and the resources available to conduct the study. The Clinical Research Networks (CRNs) and the British Association for Study of Liver Disease End of Life Specialist Interest Group will assist in the identification of sites.

12. PARTICIPANT ELIGIBILITY CRITERIA

12.1. Inclusion criteria

- Male or Female
- Age ≥18 years
- Refractory ascites (with need for recurrent LVP) defined as per International Ascites Club criteria (5-6):
 - Diuretic-resistant ascites: ascites that cannot be mobilized or the early recurrence of which cannot be prevented because of a lack of response to sodium restriction and diuretic treatment (spironolactone 400 mg and furosemide 160 mg) and or
 - Diuretic-intractable ascites: ascites that cannot be mobilized or the early recurrence of which cannot be prevented because of the development of diuretic induced complications that preclude the use of an effective diuretic dosage
- Registered with a General Practitioner (GP) in the community Trusts served by the participating centres.
- Capacity to give informed consent

12.2. Exclusion criteria

- Loculated and or chylous ascites
- Evidence of active infection that in the investigator's opinion would preclude insertion of LTAD (for example, bacterial peritonitis) such patients would need to receive appropriate treatment and could then be reconsidered
- A candidate for liver transplantation and or TIPS
- Psychosocial issues which in the opinion of the medical team will preclude study participation
- Pregnancy all women of childbearing age must have a negative pregnancy test
- Lacks capacity to give informed consent

Participants whose first language is not English can have materials translated so as not to exclude their participation. Participants will not be excluded if they are already participating in another ongoing study, as long as their researchers are confident that participation in the current study will be logistically feasible and not too onerous for the participants. Approval for co-enrolment may be needed by on-going study Chief Investigator. Patients will also not be excluded from participation in the study in relation to their place of care/residence, for e.g. if they are in or move to a hospice/ care home. Study recruitment would remain unchanged with patient identification and consent undertaken in the hospital sites and follow-up data collection in usual place of residence (including care homes).

13. STUDY PROCEDURES

13.1. Schedule of Assessments

Table 3. Schedule of Assessments

		1		1		1	1	1	1
	Screening	Telephone call	Baseline / WO (7 +/- 3 days post screening)	W2 (+/- 3 days)	× W4 (+/- 3 days)	WG (+/- 3 days)	W8 (+/- 3 days)	W10 (+/- 3 days)	W12 (+/- 3 days)
Perform capacity check using capacity checklist.	X		x	X	X	X	X	Х	X
England sites : If patient loses capacity during study, approach Consultee									
Scotland sites : Capacity to be checked at start of study only.									
Informed Consent	Х								
(Informed consent can be given prior to the screening visit but must be confirmed at the screening visit)									
Demographics	X								
Medical History	x		x						
Routine clinical blood	X		X ¹	Х	Х	Х	Х	Х	Х
(Haemoglobin, white cell count, Platelets, APPT, INR/PT, Bilirubin, ALT, Alkaline phosphatase, Total protein, Albumin, Sodium, Potassium, Urea, Creatinine, eGFR, C reactive protein)									

Pregnancy test if child bearing age	X								
Diagnostic ascitic tap (white cell count, neutrophil count and culture)	X		X ¹	X ²					
Eligibility check (inclusion/exclusion)	X		×						
Vital signs	Х		Х	X	Х	X	X	X	Х
(Temperature, blood pressure and pulse)									
(Height and weight at baseline only)									
Liver disease scores (CPS/MELD/UKELD)	x		X	X	X	X	X	X	X
Liver disease assessment and history (includes hepatic encephalopathy, variceal bleeding, ascites and hepatocellular cancer	x		X	x	x	X	X	X	X
Alcohol and substance use assessment (self -reported)	Х		Х	Х	X	X	X	Х	X
Assessment of transport methods available to patient (in case the participant is to travel for LTAD insertion)	X								
Randomisation			Х						
(Can be done up to 10 days prior to the baseline visit)									
Notification of Randomisation		X							
telephone call									
(If randomisation is done prior to baseline visit)									
	1								

Optional Research blood sample 20ml	X						
(10ml for serum, 10ml for whole blood. To be frozen at -80°C for analysis at end of study)							
LTAD/LVP insertion ³	X ³						
Prophylactic antibiotics for both LTAD and LVP groups after discussing risks/benefits	X	X	X	X	X	X	X
Referral to palliative care for both LTAD and LVP groups	X						
LTAD (group 1) research team member to collect drainage data collated by community nurses, also assess LTAD and ask about abdominal pain	X	X	X	X	X	X	X
LVP (group 2) drainage assessment to be collected from medical records.	X	X	X	X	X	X	X
Adverse event review	X	X	X	X	X	X	X
Concomitant medication review	X	X	X	X	X	X	Х
Ascites questionnaire (Ascites Q) completion (patient)	X	X	X	X	X	X	X
Liver specific HRQoL (SFLDQoL) questionnaire completion (patient)	X		X		Х		X
Generic HRQoL (EQ5D-5L) questionnaire completion (patient)	X	X	X	X	X	X	X
Care giver questionnaire (CRRS) completion (caregiver)	X		X		X		×

Community service use (modified AHCR) questionnaire completion (patient)		X	X	X	Х	Х	Х	Х
Hospital service use in house designed questionnaire completion (research team member)								X
Optional qualitative interviews (patients, informal caregivers and healthcare professionals) will be conducted throughout the study. Only one interview per participant			X	X	X	X	X	X

¹ PT and or INR and platelet count and diagnostic ascitic tap need to be checked within 7 +/-3 days of LTAD insertion; Spontaneous bacterial peritonitis defined as ascitic white cell count > 500 cells/mm³, and or neutrophil count > 250 cells/mm³ and or a positive ascitic fluid culture. (64)

² To be done in LVP group at each drainage as is current standard of care, and LTAD patients only if suspicion for peritonitis. In those with LTAD and clinical suspicion for peritonitis, take ascitic fluid sample for analysis from both from LTAD and via a separate ascitic tap

³ For LTAD only: Prior to LTAD insertion correct INR and platelet count as per local trust guidelines. If no local guidelines available use the following: if INR≥1.5 and platelet count ≤ $50x10^9$ 2 units of Fresh Frozen plasma and 1 -2 pools of platelets to be transfused prior to LTAD insertion

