Community Management of LTAD

- The community nurses will visit patients at their usual residence to carry out ascites drainage as clinically indicated but drainage episodes should be limited to a maximum of three times a week. If additional training is required, the community nursing teams should contact the LTAD manufacturer as stated above. The amount to be drained will be dependent on clinical need, but would usually be 1-2L at a time with a maximum of 5L/week. Each time drainage is performed it will be recorded by the community nurses in a drainage diary which will be kept in the patient's usual place of residence. This drainage diary data will be collected by the research team members during fortnightly home visits and entered into the electronic Case Report Form (eCRF) by a member of the research team.
- Additional drainage bags will be delivered to patients by the research team during the fortnightly home visits. The drainage bags will be disposed of in the usual way by the council as per standard arrangements in that region.
- The contact telephone number for the research team to be used "in hours" (9am-5pm) during week days will be provided to community teams. Out of hours, patients or community healthcare professionals should contact the out-of-hours GP service or the patients should attend Accident and Emergency (A&E) for emergency trial related problems.
- The community nurses will perform risk assessments during their home visits as per their usual practice and inform the research team of any concerns that have been identified as regards
 - Drain leakage or blockage
 - Cellulitis at the drain site
 - Abdominal pain not settling with usual analgesia i.e. suspicion of peritonitis
 - Anything else which in the opinion of the community nurse is directly related to the LTAD and requires hospitalisation

- Community nurses will train informal caregivers if they wish to perform drainage. Though caregivers can assist with drainage, the drainage diary will still be completed by the community nurses

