17.1. Safety Monitoring

This will include collection of routine clinical bloods, assessment of LTAD and collection of LTAD drainage data collated by community nurses (see community SOP for sample drainage diary). LVP drainage data will be collected from medical records.

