22.5. Participant Safety Monitoring

At each site an experienced research team member will visit ALL patients at home fortnightly for safety monitoring and questionnaire-based assessments. This will include assessment of abdominal pain, vital signs, LTAD and collection of routine clinical bloods (FBC, INR, renal/ hepatic profile and CRP). The research team member will collect ascites drainage data recorded by community nurses at each site. Please see SAFETY REPORTING (section 22) for adverse event reporting.

The research team member will follow guidance in the lone worker policy when conducting home/usual place of care visits.

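### Minor drain-site events (leakage, cellulitis) are looked for more closely in the LTAD arm than in the LVP arm, and Table 3 and Section 22.5 disagree on who is asked about abdominal pain

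*Protocol*

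**What the plan says.** **Research visits.** Table 3 (Section 13.1) has two arm-specific rows, each marked at baseline and at every fortnightly visit to week 12. Group 1: "LTAD (group 1) research team member to collect drainage data collated by community nurses, also assess LTAD and ask about abdominal pain". Group 2: "LVP (group 2) drainage assessment to be collected from medical records". Section 17.1 follows the same split: safety monitoring includes an assessment of the LTAD, and "LVP drainage data will be collected from medical records". Table 3 also has a row "Adverse event review" at the same time points, not restricted by arm.

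**Community nurses.** Section 16.1 has nurses attend LTAD patients at home to drain ascites as clinically indicated; "drainage episodes should be limited to a maximum of three times a week". They are to "perform risk assessments during their home visits as per their usual practice and inform the research team of any concerns" about leakage or blockage, cellulitis at the drain site, and abdominal pain that usual analgesia does not settle. No such channel is described for LVP.

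**Abdominal pain.** Section 22.5 says that all patients are visited fortnightly and, of that visit, "This will include assessment of abdominal pain, vital signs, LTAD and collection of routine clinical bloods". So this section puts the pain assessment in both arms, while Table 3 names it in the group 1 row only.

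**The concern.** Leakage and cellulitis are the events most open to detection differences. Section 22.4 describes them as usually self-limiting. In the feasibility trial none led to hospitalisation, and they were the one type of complication said to differ between arms (41% LTAD, 11% LVP in Table 5). An event that never reaches hospital is recorded only if someone looks, asks or is told. In the LTAD arm a researcher inspects the drain and a nurse sees it between research visits. In the LVP arm nobody is scheduled to look at or ask about the puncture site. Apart from the trial statistician nobody is blinded (Section 15.4), so nothing else in the design evens this out.

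At stake is the interpretation of local complications. Infections are a secondary objective, worded more widely than peritonitis, and LTAD safety is a pilot question. If LTAD shows an excess of leakage or cellulitis, the trial as scheduled could not say how much of it is detection. Unrecorded LVP-site events cannot be recovered at the analysis stage.

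**Working it through.** The plan states no figure for this, so there is none to reproduce. The check sets the two arms' ascertainment side by side, counts contacts, and then shows what an assumed gap would do.

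**1. Ascertainment by arm**

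| Source | LTAD | LVP |
|---|---|---|
| Researcher check of site (Table 3, 17.1, 22.5) | Yes, the LTAD | None named |
| Pain question, Table 3 | Yes | Not listed |
| Pain assessment, Section 22.5 | Yes | Yes |
| Ascites Q and EQ-5D-5L pain items, fortnightly | Yes | Yes |
| Adverse event review, vital signs, bloods with CRP | Yes | Yes |
| Community-nurse reports of leakage, cellulitis, pain | Yes | None |

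Pain is thus covered in both arms by several routes. Leakage and cellulitis are not: the only common source in which they would naturally surface is the adverse event review, for which the protocol gives no site question. Section 36 points the same way, since home visits shortened for COVID keep bloods and the LTAD assessment, with questionnaires by telephone.

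**2. Contacts over 12 weeks (84 days)**

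- Research visits: 7 in each arm (weeks 0, 2, 4, 6, 8, 10, 12).
- Community-nurse drainages, LTAD: at most 3 × 12 = 36. This is a ceiling.
- LVP attendances at the 10 to 14 day interval given in Section 8: 84/14 = 6 to 84/10 = 8.4.

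**3. Illustration for local events (assumed capture rates)**

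With equal true rates, apparent risk ratio = LTAD capture / LVP capture.

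- LVP capture: assume 50% to 80% of episodes are volunteered at adverse event review, so 20% to 50% are missed.
- LTAD capture: nurse visits 2 to 3 times a week are 3.5 to 2.3 days apart. A 3-day episode is seen with probability 3/3.5 = 0.86 at the wider spacing and with certainty at the closer one.
- Complete LTAD capture: 1/0.80 = 1.25 to 1/0.50 = 2.0.
- LTAD capture of 0.86: 0.86/0.80 = 1.08 to 0.86/0.50 = 1.72.

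Against the feasibility ratio of 41/11 = 3.7: if that trial had the same gap (also assumed) and complete LTAD capture, the LVP rate would be 11/0.80 = 13.75% to 11/0.50 = 22%, and the ratio 41/13.75 = 3.0 to 41/22 = 1.9. Detection could alter the size of the excess but would not, on these assumptions, remove it.

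**4. Peritonitis**

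Section 16.1 has LVP fluid analysed at each drainage and LTAD fluid only on clinical suspicion, and a raised cell count or positive culture alone is diagnostic. Symptom-free cases can be found in LVP and missed in LTAD. If true risk were equal at 6% to 12.7% and LTAD detected 70% to 85% of what routine testing finds (assumed), observed LTAD incidence would be too low by 0.06 × 0.15 = 0.9 points to 0.127 × 0.30 = 3.8 points. This favours LTAD, the opposite direction.

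**The case against.** Three stronger readings are tempting, and the documents support none of them.

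- *A reader might infer that pain is checked in LTAD only.* Section 22.5 applies it to all patients, and Ascites Q and EQ-5D-5L ask about pain fortnightly in both arms. What stands is the disagreement between Table 3 and Section 22.5.
- *A reader might infer that LVP complications are taken from medical records.* The records are named for drainage data. Adverse event review is scheduled in both arms.
- *A reader might infer that the infection comparison is biased against LTAD.* Cumulative peritonitis incidence is the only named infection outcome, and its testing rule runs mainly the other way. A smaller opposing effect is possible, because suspected LTAD cases are also sampled from the drain, where the protocol expects skin contaminants.

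It can also fairly be said that part of the asymmetry is inherent. A tunnelled device stays in place, whereas an LVP drain is temporary, and the nurses are there to deliver the intervention. LVP patients also return to hospital every 10 to 14 days. Leakage and cellulitis are not listed endpoints, and events leading to hospitalisation should come to light in either arm. The eCRF and the home-visit SOP are not at hand and may contain prompts. All this limits the weight of the point. It does not supply a puncture-site question for LVP in the schedule, and the self-limiting events at issue are those that need not reach hospital.

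**Conclusion.** The point holds in a limited form. Minor drain-site events are ascertained unequally: LTAD has a scheduled researcher check and a community-nurse reporting channel, and LVP has no named counterpart beyond the adverse event review. In this unblinded trial, leakage and cellulitis are likely to be recorded more fully in LTAD. The size cannot be derived from the documents. The apparent risk ratios of about 1.1 to 2.0 rest wholly on assumed self-report and detection rates and only show that the effect need not be trivial. The conclusion covers neither peritonitis nor the primary outcome. Separately, Table 3 and Section 22.5 contradict each other on the abdominal-pain question and must be reconciled. This is a cheap improvement to make prospectively. It does not threaten the trial's main conclusion.

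**What to change.** 1. Add one common item to Table 3 at every fortnightly visit in both arms: abdominal pain, leakage, and redness or infection at the drain or puncture site since the last visit, with a brief look at the LTAD exit site or the most recent LVP site.
2. Align Sections 17.1 and 22.5 with that item, which also settles the disagreement on pain.
3. Record for each event who first detected it (common visit, community nurse, hospital).
4. Report all events by arm as the safety result. Add a supportive comparison limited to events identified at the common visits or treated in hospital. Nurse-detected LTAD events should not be taken out of the main safety result, because that could understate true harm from the drain.

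The cost is wording in three places, a short eCRF checklist with a source field, and a few extra minutes per LVP visit. Section 16.2 keeps home visits to research tasks so that they do not affect quality of life in group 2, so the item should be written into the home-visit SOP as a research task. The change narrows the gap without closing it. With a look every 14 days, an episode of 3 to 7 days that is volunteered with probability 0.5 to 0.8 is still missed with probability (1 − 7/14)(1 − 0.8) = 10% to (1 − 3/14)(1 − 0.5) = 39%. Asking directly about the whole interval should improve on unprompted reporting.
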